11.3 Criteria for Discontinuation of Protocol Treatment

Protocol treatment will be discontinued if the patient

- has progression of disease so that SBRT is not a reasonable treatment;
- becomes inoperable for radical surgical resection;
- cannot tolerate SBRT treatment;
- wants to withdraw from the study

If protocol treatment is discontinued, follow up and data collection will continue as specified in the protocol.

12.0 DATA COLLECTION (6-AUG-2018)

Translation of data forms is critical. The institution is responsible for all translation costs. All data forms below must be provided in English and in the native language. Certification of the translation is optimal but due to the prohibitive costs involved, RTOG will accept, at a minimum, a verified translation. A verified translation consists of the actual data form in English and in the native language, along with a cover letter on organizational/letterhead stationery that includes the professional title, credentials, and signature of the translator as well as signed documentation of the review and verification of the translation by a neutral

third party. The professional title and credentials of the neutral third party translator must be specified as well.

Data should be submitted to:

RTOG Headquarters*
[name]
Philadelphia, PA 19103

***If a data form is available for web entry, it must be submitted electronically.**

Patients will be identified by initials only (first middle last); if there is no middle initial, a hyphen will be used (first-last). Last names with apostrophes will be identified by the first letter of the last name.

12.1 Summary of Data Submission (6-AUG-2018)

Item	Due
Initial Evaluation Form (I1) Pathology Report (P1)	Within 2 weeks of registration
Radiotherapy Form (T1)	Within 1 week of RT end
Surgical Form (S1) Surgical Procedure Report (S2) Surgical Pathology Report (S5) NOTE: The S2 and S5 should be de-identified and emailed to [contact] as PDF files	Within 4 weeks after protocol surgery
Follow-up Form (F1)	Every 3 months for years 1-2 years, every 6 months for year 3, then annually until publication of study results

12.2 Summary of Dosimetry Digital Data Submission (Submit to RTOG Headquarters; see Section 12.2.1) (6-AUG-2018)

Item	Due
Preliminary Dosimetry Information (DD) Digital Data Submission – Treatment Plan submitted in DICOM format to RTOG via TRIAD, exported from treatment planning machine by Physicist Digital data submission includes the following: 
• Planning CT• RT Structure File including all required tumor volumes and critical normal structures• RT Plan File for final plan• RT Composite Dose File for treated beams• Digital DVH data including all required tumor volume and critical normal structures• Digital Data Submission Form (DDSI) [on the RTOG website, Foundation study 3502, under Forms]	Within 1 week of start of RT

Final Dosimetry Information Radiotherapy Form (T1) Daily Treatment Record (T5) [Copy of daily treatment chart submitted via email to [contact].]	Within 1 week of end of RT
PET and/or CT progression scans (MR) PET and/or CT progression reports (ME) Digital Data Submission Form (DDSI) [on the RTOG web site, Foundation study 3502, under Forms]	At time of progression
NOTE: For all digital data submissions (preliminary, final Dosimetry or PET/CT scans for progression), sites must complete a Digital Data Submission Form (DDSI) via the RTOG web site. Also, sites will notify RTOG via e-mail [contact] after any digital data is submitted. The e-mail must include study number, site name, and case numbers.	
Modified digital patient data as required by RTOG will be submitted via TRIAD.	

12.2.1 Digital Data Submission to RTOG Headquarters

Digital data will be submitted to RTOG via TRIAD.

12.2.2 Method of Plan Submission

Sites will follow directions for establishing a TRIAD account for the purpose of submitting digital RT data. Refer to the RTOG website for instructions.

<http://www.rtog.org/ClinicalTrials/RTOGFoundationStudies/RTOGFoundationStudy3502.aspx>,

13.0 STATISTICAL CONSIDERATIONS

13.1 Primary Endpoint

13.1.1 Two-year local-regional tumor control, which is defined as freedom from local-regional recurrence after RODS and freedom from progression of local primary tumor and disease occurrence at nodal regions after SBRT (see Section 11.2.2)

13.2 Secondary Endpoints

13.2.1 Overall survival;

13.2.2 Disease-free survival;

13.2.3 Frequency of site-specific failure (patterns of failure);

13.2.4 Time to local-regional tumor failure and distant metastases;

13.2.5 PET tumor response;

13.2.6 Frequency of adverse events, graded by CTCAE, v. 4;

13.2.7 Trial feasibility parameters.

13.3 Sample Size

This randomized phase II trial will compare SBRT and RODS among patients with T1N0M0 NSCLC.

The trial is designed to determine whether there is a 15% or smaller absolute decrement in local-regional tumor control at 2 years for SBRT relative to RODS. Specifically, we assume that patients treated with RODS will have 90% of 2 year local regional control, and aim to demonstrate that those with SBRT would have no greater than 15% lower local-regional control largely due to lack of nodal dissection, or 75% local-regional control. The rationale for permitting up to 15% lower 2-year local tumor control for the SBRT arm is that SBRT is expected to have equivalent survival as such local failure would be effectively salvaged by surgery, radiation, chemotherapy or combined trimodality therapy [252]. Additionally, we expect the patients treated with SBRT would

have a better quality of life and more favorable toxicity profiles (less severe treatment complications such as inter-operative death). The null hypothesis is that SBRT has a > 15% lower local-regional control rate, and the alternative is that the difference is 15% or less. To ensure probability of 0.80 for correctly concluding that the difference is 15% or less (that is, when this is the true state) and probability 0.20 of falsely concluding that the difference exceeds 15%, 36 patients per treatment arm is required, a total of 72 patients. To account for ineligible patients and attrition of the cohort during the 24-month follow up, a 5% inflation of the sample size is applied, leading to a **total of 76 patients**. With 24 months of accrual and a minimum follow-up of 24 months, the trial will be completed.

13.4 Accrual

Five institutions will participate in this trial. It is estimated that 100 patients in each participating center will undergo a complete resection for stage I NSCLC each year. Of these patients, 5-10% are expected to consent to enroll on this trial. Thus, we anticipate that enrollment will be completed in 24 months. We plan to report primary results at a maximum of 2 years after the last patient has been enrolled (i.e. when all patients have accumulated either 2 years of follow up or a primary endpoint failure event).

13.5 Analysis Methods

13.5.1 Primary Endpoint

A test of binomial proportions will be used to compare local-regional failure proportions between treatment arms. If despite randomization, there are imbalances in important patient and disease covariates, then logistic regression will be used to estimate the effect of treatment accounting for other covariates [253]. Survival analysis methods, specifically the Cox proportional hazards model and the cumulative incidence function, will be used to evaluate the time to local-regional failure hazard by treatment arm and the cumulative probability of local-regional failure events over time by treatment arm [254].

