Data on quality of life (QOL) is limited after SBRT for NSCLC. For stage I NSCLC, QOL was assessed in 39 patients treated with SBRT by using The European Organization for Research and Treatment of Cancer Quality of Life Questionnaire (EORTC QLQ) C30 and the QLQ LC13 lung cancer-specific questionnaire. Assessments were done before treatment, at 3 weeks, and at 2, 4, 6, 9, and 12 months after treatment, and until death or progressive disease. Toxicity was evaluated using CTCAE, v. 3.0. Emotional functioning improved significantly after treatment. Other functional scores, QLQ C30, and QLQ LC13 lung symptoms (such as dyspnea and cough) showed no significant changes. [164]. These results may be better than those reported for 3DCRT, RFA, and surgical resection. Using Markov model analysis, a recent cost effectiveness study report indicates that SBRT may offer comparable OS and quality-adjusted life expectancy as compared with surgical resection [266]. Randomized prospective studies comparing surgery vs. SBRT in early-stage lung cancer are warranted to further investigate the relative survival, quality of life, and cost characteristics of both treatment paradigms [266].

In this trial, quality of life endpoints will not be evaluated; however, provided that the primary hypothesis and performance metrics are satisfied, the subsequent phase III trial will incorporate detailed QOL measures in order to definitively and comprehensively evaluate SBRT for larger scale clinical utility.

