2.0 OBJECTIVES

2.1 Primary Objective

2.1.1 The primary aim of this study is to determine whether SBRT provides local-regional tumor control that is not more than 15% lower than RODS. This difference is considered a threshold deficit at which overall survival (OS) will not be compromised.

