13.5.2 Other Time-to-Event Endpoints and Sites of Failure

The Kaplan-Meier estimator and logrank test will be used to estimate survival distributions and compare survival by treatment arm. The hazard rate ratio with 95% confidence interval will be estimated via the Cox proportional hazards model. If the proportionality assumption is not met, then other models will be considered as appropriate. Contingency table methods and logistic regression will be used for discrete endpoints such as site-specific failure proportions and PET response. Cumulative incidence of time to local-regional failure, other site-specific failure (i.e., distant metastases), and cause-specific survival will be estimated using appropriate competing risks methods. Models for cause-specific hazards and cumulative incidence of these events will be used to estimate different aspects of the relative event-specific failure risk between groups [255] [256]. PET tumor response (Section 11.2.1.2) and an evaluation of assessment of failure patterns after SBRT and RODS (Section 11.2.3) will be investigated.

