13.6 Data Monitoring Committee, Interim Analyses, and Stopping Criteria

An independent Data Monitoring Committee will be constituted to oversee this trial. Accrual, other study conduct parameters, and adverse events will be reviewed at semi-annual meetings of this committee.

One formal analysis for futility with respect to demonstrating noninferiority will be performed after completion of enrollment and follow up to 1 year, including only those patients who have reached the 2-year follow-up time point. Early reporting will be considered if the estimated 2-year local-regional control rate in the SBRT arm (Arm 2) is less than 60% (in which case the exact upper one-sided 95% confidence bound would fall below 75%, the threshold noninferiority value for this trial), and if this rate is more than 15% lower than the observed rate in the RODS arm (Arm 1).

Results for dissemination will be developed, and a manuscript drafted for review, approval, and submission. After manuscript acceptance, patient follow up will be discontinued and the trial terminated. It is anticipated that termination will occur approximately 5.5 years from initiation of patient entry. This time-frame may be extended depending on factors such as the observed accrual and event rates, in which case a new trial termination date will be established.

REFERENCES

1. Jemal, A., et al., *Cancer statistics, 2009*. CA Cancer J Clin, 2009. **59**(4): p. 225-49.
2. Yang, B.H., et al., *Cancer burden and trends in the Asian Pacific Rim region*. Asian Pac J Cancer Prev, 2004. **5**(2): p. 96-117.
3. Pisani, P., D.M. Parkin, and J. Ferlay, *Estimates of the worldwide mortality from eighteen major cancers in 1985. Implications for prevention and projections of future burden*. Int J Cancer, 1993. **55**(6): p. 891-903.
4. Rami-Porta, R., et al., *The IASLC Lung Cancer Staging Project: proposals for the revision of the T descriptors in the forthcoming (seventh) edition of the TNM classification for lung cancer*. J Thorac Oncol, 2007. **2**(7): p. 593-602.
5. Hsu, C.P., et al., *Surgical-pathologic factors affect long-term outcomes in stage IB (pT2 N0 M0) non-small cell lung cancer: a heterogeneous disease*. J Thorac Cardiovasc Surg, 2009. **138**(2): p. 426-33.
6. Iwasaki, A., et al., *Results of video-assisted thoracic surgery for stage I/II non-small cell lung cancer*. Eur J Cardiothorac Surg, 2004. **26**(1): p. 158-64.

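### The risk of falsely declaring SBRT non-inferior is never set: the 0.20 in 13.3 is only the complement of its 0.80, and 13.5.1 names no test against the 15-point margin

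*Combined protocol and SAP*

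**What the plan says.** The aim is clear. Section 2.1.1 sets out to "determine whether SBRT provides local-regional tumor control that is not more than 15% lower than RODS". Section 13.3 makes this a hypothesis: "The null hypothesis is that SBRT has a > 15% lower local-regional control rate", with 15 points or less as the alternative. It assumes 90% two-year local-regional control after RODS and puts SBRT at the margin at 75%. So the null, the margin and the direction are all stated.

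Two error probabilities follow in 13.3: "To ensure probability of 0.80 for correctly concluding that the difference is 15% or less" and "probability 0.20 of falsely concluding that the difference exceeds 15" percent. From these the plan derives 36 per arm, 72 in total, raised to 76.

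For the final analysis, 13.5.1 states: "A test of binomial proportions will be used to compare local-regional failure proportions between treatment arms". It then adds covariate-adjusted logistic regression, a Cox model and cumulative incidence. None of these carries a level or a bound.

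Two levels appear elsewhere:

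- **Section 13.6**, for early reporting: "the exact upper one-sided 95% confidence bound would fall below 75%, the threshold noninferiority value for this trial".
- **Section 13.5.2**, for other time-to-event endpoints: "The hazard rate ratio with 95% confidence interval will be estimated via the Cox proportional hazards model".

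**The concern.** Under the null in 13.3, a type I error means declaring SBRT within 15 points of RODS when it is not. The 0.20 in 13.3 describes the opposite mistake, concluding that the deficit exceeds 15 points when it does not. That is the type II error, which the 0.80 already fixes. One error rate is therefore given twice and the other not at all.

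Section 13.5.1 does not repair this. Comparing two failure proportions, without more, is ordinarily a test of no difference, which is a different null from the one in 13.3. Even if a margin test is understood, the plan gives no level at which it is passed.

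At stake is whether the primary objective is met. Section 1.2.3 says that "provided that the primary hypothesis and performance metrics are satisfied, the subsequent phase III trial will incorporate detailed QOL measures", and 1.3.1 says the same of translational endpoints. A condition of that kind needs a rule fixed before the data are seen.

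**Working it through.** **Inputs from 13.3.** RODS control 0.90; SBRT control at the margin 0.75; margin 0.15; power 0.80; 36 per arm. The alphas and the true SBRT rates used below are assumptions, because the plan states neither. Normal quantiles: z(0.80) = 0.8416, z(0.90) = 1.2816, z(0.95) = 1.6449.

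**1. Reproducing 36 per arm.**

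*Equality test, 90% v 75%, one-sided 0.20, pooled variance, no continuity correction.* The mean rate is 0.825.

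n = [z(1−α)·√(2·0.825·0.175) + z(0.80)·√(0.90·0.10 + 0.75·0.25)]² / 0.15²
= [0.8416·(0.5374 + 0.5268)]² / 0.0225 = **35.65**, rounded up to 36.

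This matches, but its null is no difference between the arms.

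*Margin test, 90% in both arms.*

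n = (0.09 + 0.09)·[z(1−α) + z(0.80)]² / 0.15² = 8·[z(1−α) + 0.8416]²

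| One-sided alpha | n per arm |
|---|---|
| 0.20 | 22.67 |
| 0.10 | **36.06** |
| 0.05 | 49.46 |

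Only 0.10 comes near 36, and strictly it rounds up to 37.

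*Margin test at one-sided 0.20 with true SBRT control 87.5%.* The distance to the margin is 0.15 − 0.025 = 0.125:

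n = (0.09 + 0.109375)·(1.6832)² / 0.125² = 36.2.

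So 36 per arm does not identify the test, the alpha or the assumed SBRT rate. The inflation does check: 72/0.95 = 75.8, or 76.

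**2. One data set, two verdicts.** Take 3/36 failures on RODS and 5/36 on SBRT, an observed difference of 2/36 = 0.0556. The Farrington-Manning score test fits both failure rates subject to a difference of exactly 0.15, which gives 0.0595 and 0.2095.

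SE = √[(0.0595·0.9405 + 0.2095·0.7905)/36] = 0.0784
z = (0.0556 − 0.15)/0.0784 = −1.20, one-sided p = 0.114.

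This passes at 0.20 and fails at 0.10. As confidence limits, the score upper bound is 12.0 points at one-sided 80% and 15.7 points at one-sided 90%.

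**3. How often this happens.** The same score test was applied to all 37 × 37 outcomes, weighted by binomial probabilities with RODS control at 90%. A pass at 0.10 implies a pass at 0.20, so the last column is the difference between the two before it.

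| True SBRT control | Pass at 0.20 | Pass at 0.10 | Verdict depends on alpha |
|---|---|---|---|
| 90% | 0.8885 | 0.7837 | 0.105 |
| 85% | 0.6516 | 0.4951 | 0.157 |
| 80% | 0.3863 | 0.2497 | 0.137 |
| 75% | 0.1893 | 0.1028 | 0.087 |

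The bottom row is the false-pass risk at a true 15-point deficit: 18.9% or 10.3%.

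**4. Power at 36 per arm, 90% in both arms.** The normal approximation is Φ(0.15/√(0.18/36) − z(1−α)) = Φ(2.121 − z(1−α)).

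| One-sided alpha | Exact score test | Normal approximation |
|---|---|---|
| 0.20 | 89% | 90% |
| 0.10 | 78% | 80% |
| 0.05 | 63% | 68% |

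**The case against.** The strongest reply is that the plan, read as a whole, nearly says it all. The null, margin and direction are in 13.3. The number 0.20 is there too, and 36 per arm reproduces with 0.20 as a one-sided alpha, so the sentence may be a slip for an intended alpha of 0.20. A level that liberal can be defended in a 76-patient phase II trial meant to inform a later definitive one.

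Much of this stands. A reader might infer that the plan lacks a non-inferiority hypothesis altogether; 13.3 shows that it has one. A reader might also treat every conventional alpha as equally open. The sample size argues against that: at 90% in both arms, a margin test at one-sided 0.05 would need 50 per arm, so setting 0.20 against 0.05 would exaggerate the effect. Nor does any section say that a non-significant equality test would count as success, so that cannot be charged to the plan. Sections 1.2.3 and 1.3.1 condition the content of a later trial; they do not set an automatic go or no-go.

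The slip reading still does not close the gap. As worded, 0.20 is the wrong error. The calculation in which 0.20 gives 36 tests equality, and against the stated margin with 90% in both arms it gives 23. Section 13.6 does not help either. Its bound sets the SBRT rate against a fixed 75%, with a further condition on the observed gap between arms, and serves an interim futility look. The 95% interval in 13.5.2 belongs to a hazard ratio for other endpoints.

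**Conclusion.** The point holds in this form: the hypothesis is stated, but its type I error, the true SBRT rate behind the power, and the final decision rule are not. The error sentence in 13.3 is wrong for the null it accompanies, and 13.5.1 does not name a test of that null.

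The choice between 0.20 and 0.10 alone decides the verdict in roughly 9% to 16% of trials over true SBRT control of 75% to 90%, and it moves the false-pass risk at the margin between 18.9% and 10.3%. These figures assume RODS control of 90%, 36 evaluable patients per arm and the score test; another margin-based method would shift them somewhat. The sponsor may choose 0.20, but has to say so. Because this is the success criterion for the primary endpoint, it should be corrected before the final analysis.

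**What to change.** **Section 13.5.1.** Replace the first sentence with a rule: SBRT is non-inferior if the upper limit of the one-sided 100(1−α)% confidence interval for the difference in two-year local-regional failure (SBRT minus RODS), by a named margin-based method such as Farrington-Manning, is below 15 percentage points.

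**Section 13.3.** Replace the 0.80/0.20 sentence with three statements: the one-sided alpha, defined as the probability of falsely declaring non-inferiority when SBRT control is 15 points below RODS; the assumed true SBRT rate; and the power that follows at 36 per arm, with the method of calculation named.

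**Section 13.6.** Say whether the one-sided 95% level there also governs the final comparison. If it does, power with 90% in both arms is 63% by the exact score test (68% by the normal approximation), not 80%.

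**Cost.** One wording amendment and minor programming, with no new data and no added enrolment. The drawback is that the stated power may fall below 0.80 if a stricter alpha is named, or if the assumed SBRT rate is below 90%.

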13.5.2 Other Time-to-Event Endpoints and Sites of Failure

The Kaplan-Meier estimator and logrank test will be used to estimate survival distributions and compare survival by treatment arm. The hazard rate ratio with 95% confidence interval will be estimated via the Cox proportional hazards model. If the proportionality assumption is not met, then other models will be considered as appropriate. Contingency table methods and logistic regression will be used for discrete endpoints such as site-specific failure proportions and PET response. Cumulative incidence of time to local-regional failure, other site-specific failure (i.e., distant metastases), and cause-specific survival will be estimated using appropriate competing risks methods. Models for cause-specific hazards and cumulative incidence of these events will be used to estimate different aspects of the relative event-specific failure risk between groups [255] [256]. PET tumor response (Section 11.2.1.2) and an evaluation of assessment of failure patterns after SBRT and RODS (Section 11.2.3) will be investigated.

13.5.3 Adverse Events

Frequency distributions of specific adverse events of interest will be compared between treatment arms using Fisher's exact test. If there appear to be imbalances in patient or disease characteristics by treatment arm, then stratified methods or logistic regression modeling will be used to compute adjusted tests. Logistic regression modeling will be used to explore the relationship between treatment toxicities and other factors in addition to treatment.

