2.2 Secondary Objectives

2.2.1 To qualitatively and quantitatively assess feasibility of this joint RTOG-China clinical trial. Parameters to be assessed include satisfaction of pre-registration requirements (e.g. surgical and RTQA credentialing), patient accrual rate, patient eligibility rate, randomization conduct baseline forms completion and timeliness, follow-up forms completion/delinquency, and loss to follow-up rate;

2.2.2 To compare overall survival and disease-free survival between study arms;

2.2.3 To estimate and compare time to local-regional failure, time to distant metastases, and patterns of failure between study arms;

2.2.4 To compare treatment toxicities using the Common Terminology Criteria for Adverse Events (CTCAE, v. 4) between study arms; specific comparisons will include adverse events at 1, 3, 12, 24, and 36 months post-therapy;

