Patients enrolled to this study should have pulmonary function tests (PFTs), including Forced Expiratory Volume in 1 second (FEV1), Forced Vital Capacity (FVC), and Diffusing Capacity for Carbon Monoxide (DLCO). The CTCAE, v. 4 includes specified criteria for grading adverse events related to PFT parameters. The grading criteria for PFT changes use the "percent predicted" values from 0-100% which are recorded on the patient's PFT report. A percent predicted of 90% conveys that the patient is able to perform the PFT test to a result that is 90% of what would be expected for the normal general population of the same height, age, and sex. The CTCAE, v. 4 grading criteria for PFTs assumes that all patients have normal baseline pulmonary function, which is often not true for lung cancer patients. In this study we will use RTOG protocol specific toxicity classification for PFTs that adjusts for baseline abnormalities. Changes that occur after therapy will be referenced to the baseline for a given patient, which will be abnormal for most patients. This scale defines a proportional decline from the baseline. Grade 1 toxicity will be a decline from baseline to a level 0.90 times the baseline, grade 2 will be a decline to a level $0.75 \times$ baseline, grade 3 will be a decline to a level 0.5 of baseline, grade 4 will be a decline to a level $0.25 \times$ baseline, and grade 5 will be death. This scheme is depicted in the table below.

As an example, a patient who enters the study with a percent predicted DLCO of 55% who experiences a post treatment decline to a percent predicted DLCO of 40% would have a grade 4 event in the original CTCAE, v. 4 criteria; however, under the modified PFT toxicity classification for patients with abnormal baseline, his decline would constitute a decrease to 0.72 of the baseline value which is between 0.75 and 0.5 or a grade 2 event.

RTOG Pulmonary Function Test Toxicity Scale					
Adverse Event	Grade				
	1	2	3	4	5
FEV-1 Decline	0.90-0.75 times the patient's baseline value	<0.75-0.50 times the patient's baseline value	<0.50-0.25 times the patient's baseline value	<0.25 times the patient's baseline value	Death
FVC Decline	0.90-0.75 times the patient's baseline value	<0.75-0.50 times the patient's baseline value	<0.50-0.25 times the patient's baseline value	<0.25 times the patient's baseline value	Death

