6.8.1 Adverse Events (AEs)

Definition of an AE: Any unfavorable and unintended sign (including an abnormal laboratory finding), symptom, or disease temporally associated with the use of a medical treatment or procedure regardless of whether it is considered related to the medical treatment or procedure (attribution of unrelated, unlikely, possible, probable, or definite).

AEs, as defined above, experienced by patients accrued to this protocol should be reported on the AE section of the appropriate case report form (see Section 12.1).

NOTE: If the event is a Serious Adverse Event (SAE) [see next section], further reporting will be required. Reporting AEs only fulfills Data Management reporting requirements.

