9.1.1 Cytotoxic Therapy

Cytotoxic therapy is not recommended for patients with stage IA (T1N0) disease. Patients with unexpected pathologic stage II or III disease should be offered adjuvant cisplatin-based chemotherapy, although there will be no primary, chemotherapy-related endpoints for this trial. Adjuvant chemotherapy for patients with stage IB NSCLC is controversial [188-191] but is sometimes offered to patients with higher-risk T2 tumors (> 4 cm) in routine clinical practice. To be consistent for trial treatment, adjuvant therapy is not recommended for patients with

clinical stage T1N0 and pathologic stage T2N0 tumors. The adjuvant chemotherapy regimen and the timing of chemotherapy will be at the discretion of the treating oncologist. However, docetaxel and gemcitabine containing regimens should be avoided due to concerns of exacerbating radiation lung injury. Otherwise, any cisplatin/carboplatin-based 2-drug regimen is considered acceptable (e.g. cisplatin/etoposide, carboplatin/paclitaxel, cisplatin/paclitaxel, cisplatin/pemetrexed, carboplatin/pemetrexed, cisplatin/vinorelbine).

9.1.2

Salvage Therapy

If a patient has disease progression after trial treatment (either RODS or SBRT), salvage therapy should be implemented per standard of care. Salvage therapy could include multimodality care, such as surgical resection, radiation (including SBRT) and systemic therapy based on the stage of the disease, per NCCN guidelines.

9.2

Non-permitted Supportive Therapy

9.2.1

Molecularly Targeted Therapy

No molecularly targeted therapy is planned for the patients treated on this trial. The addition of molecularly targeted therapy is not permitted, except in the setting of another clinical trial or progression of disease. Patients may be entered on appropriate trials of adjuvant therapy with either cytotoxic or molecularly targeted therapy.

9.2.2

Other Cancer Therapy

Aside from the therapy outlined above for surgical resection, SBRT, and systemic therapy, patients must not receive other concomitant local or regional antineoplastic therapy (including standard fractionated radiotherapy, non-approved systemic therapy, and surgery except as described in this protocol) except at disease progression.

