APPENDIX II: STUDY PARAMETER TABLE: *See section 11.1 for details and exceptions

Assessments	Within 6 wks prior to registration, unless otherwise noted	Arm 1				Arm 2				Both Arms
		Prior to surgery in clinic OR Pre-Op OR prior to surg.remove of tumor	Intra-Op after surgical removal of tumor	Prior to dis-charge	4-6 wks Post-Op	Prior to 1st fraction of SBRT	After 3 rd fraction of SBRT	After all SBRT (the last day)	4-6 weeks after end of SBRT	
History & Physical	X				X				X	X
Thoracic Surgeon evaluation	X									
Document weight	X				X				X	X
Performance Score	X				X				X	X
PFTs (with DLCO)	X									X*
FDG-PET/CT scan	Within 4 wks				X					At 3, 12, 24 mos.
CT of chest/upper abdomen, with contrast	Within 4 wks				X					Chest CT with contrast at 3,6,9, 12, 18, 24, 36 mos.
EBUS	Within 4 wks prior to treatment									
Adverse event assessment					X			X	X	X
Pregnancy test, if applicable	Within 72 hrs.									
†Blood for research		X	X	X	X	X	X	X	X	
†Tissue for banking	For Both Arms: prior to treatment									

†For patients who consent to participate in the specimen banking component of the study; see Appendix I.

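### CTCAE symptoms have no pre-treatment grade, so symptoms already present can be counted as toxicity in both arms and dilute the toxicity comparison

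*Combined protocol and SAP*

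**What the plan says.** Objective 2.2.4 is to compare treatment toxicities under CTCAE v. 4, and adds that "specific comparisons will include adverse events at 1, 3, 12, 24, and 36 months post-therapy". The analysis rule is in Section 13.5.3: "Frequency distributions of specific adverse events of interest will be compared between treatment arms", by Fisher's exact test. It allows adjusted tests if patient or disease characteristics look unbalanced, and exploratory logistic models with further factors. It names no baseline grade, grade threshold, time window or use of attribution.

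In Appendix II the row "Adverse event assessment" has no mark in the pre-registration column, the pre-surgery column or the column before the first SBRT fraction. Its marks are at 4-6 weeks post-op (Arm 1), on the last SBRT day and 4-6 weeks later (Arm 2), and in follow-up (both arms).

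Section 6.8.1 defines an adverse event by its timing, "regardless of whether it is considered related to the medical treatment or procedure". It then lists five levels of attribution, which Section 13.5.3 does not use.

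For pulmonary function the protocol does deal with baseline. Section 6.7.3 observes that CTCAE grading "assumes that all patients have normal baseline pulmonary function, which is often not true for lung cancer patients", and it grades FEV1, FVC and DLCO as a proportion of the patient's own starting value.

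On later therapy, Section 9.1.1 states: "Patients with unexpected pathologic stage II or III disease should be offered adjuvant cisplatin-based chemotherapy". Section 9.1.2 states: "Salvage therapy could include multimodality care, such as surgical resection, radiation (including SBRT) and systemic therapy".

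**The concern.** The objective concerns toxicity caused by treatment, while the planned test counts events recorded after treatment. Without a pre-treatment grade, a cough recorded at 3 months may be new, worse or unchanged. Section 6.7.3 accepts that lung function will be abnormal at baseline in most of these patients and corrects for it. Cough, dyspnea and fatigue, which Section 6.7.1 lists as possible SBRT effects, get no such correction. Follow-up PFTs are at the physician's discretion (Section 11.1.1.2), so the corrected measure may also be incomplete.

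The comparison matters more than most secondary ones. Section 13.3 supports the 15-point margin partly by expecting better quality of life and less severe toxicity with SBRT. Section 1.2.3 says quality of life will not be evaluated, so toxicity is the only one of those two benefits that the trial measures.

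**Working it through.** **Group size.** Section 13.3 gives 36 per arm, 72 in total. A one-sided 0.20 test of 90% v 75% with 80% power gives 36 per arm, so the figure reproduces. With 5% inflation, 72/0.95 = 75.8, rounded up to 76, or 38 per arm. The plan states no power for toxicity, so everything below is illustrative.

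**Assumed inputs, not in the documents.** New-onset risk p is 30% (RODS) and 10% (SBRT) for one symptom. The test is Fisher's, two-sided 5%. A share b of each arm has the symptom before treatment, and every such patient is counted.

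**As written.** The recorded proportion in an arm is b + (1 − b)p, so the difference between arms is (1 − b) × 20 points. Power is exact, summed over both binomial distributions.

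| b | RODS | SBRT | Difference (points) | Power, 38 per arm |
|---|---|---|---|---|
| 0% | 30.0% | 10.0% | 20 | 50% |
| 5% | 33.5% | 14.5% | 19 | 40% |
| 10% | 37.0% | 19.0% | 18 | 34% |
| 20% | 44.0% | 28.0% | 16 | 23% |

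At 36 per arm the powers are 47%, 38%, 31% and 21%. At 38 per arm with b of 30% or 40%, power is 17% or 13%, but prevalences that high are plausible only for mild symptoms.

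**Direction.** The same b enters both arms, so the difference shrinks and does not change sign. If p is 10% in both arms, the recorded rates stay equal (14.5% v 14.5% at b = 5%). A chance imbalance is possible: at b = 20% the standard deviation of the between-arm difference in baseline prevalence is √(2 × 0.2 × 0.8 / 38) = 9 points. Section 13.5.3 could not adjust for it without a recorded baseline grade.

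**Severe events.** Grade 3 or higher symptoms should be rare at entry. Patients are Zubrod 0-1 (Section 3.1.6) without baseline hypoxemia (Section 3.1.3), and Table 6c places dyspnea at rest at grade 3. With b of 1% or 2% in the formula above, power is 48% or 46% instead of 50%.

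**After the fix.** If patients with a prior symptom worsen as often as others develop it, the proportions return to 30% v 10% and power to 50%. If none of them can worsen, the proportions are (1 − b)p. At b = 20% that is 24% v 8%, with power 38%. Both exceed the 23% obtained as written.

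**The case against.** Several points on the other side stand. Randomization means prior symptoms do not count against one arm. PFT events already have a baseline rule, and Table 6c excludes other causes for pneumonitis grades 1-2. The severe complications behind the toxicity argument in Section 13.3, and the 10-30% grade 3 rate for RODS in Section 1.4, are hardly affected. An Initial Evaluation Form is due within 2 weeks of registration (Section 12.1) and case report forms carry grading instructions (Section 6.8). Their content is not shown, so baseline symptoms may be noted somewhere. None of this puts a graded baseline in the schedule or a rule for it in Section 13.5.3.

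A reader might infer something stronger: that because counting does not stop at adjuvant or salvage therapy, the analysis is biased and its main version should end there. The documents do not support that.

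- Such therapy can differ by arm. Pathologic upstaging is found only at resection, and salvage will be more frequent after SBRT if its control is lower. But counting all events by assigned arm is a legitimate treatment-policy comparison, and adjuvant chemotherapy is a consequence of surgical staging.
- The effects oppose each other. Take 30% v 10% again and combine risks as 1 − (1 − own risk)(1 − added risk). Salvage in 10% v 25% of patients, with 40% of those having an event, gives 32.8% v 19.0%, a difference of 13.8 points. Adjuvant chemotherapy in 10% of RODS patients alone, with 30-50% having an event, raises the difference to 22.1-23.5 points. The event rates and the upstaging rate are assumptions.
- The 25% SBRT failure rate is the non-inferiority limit, not a forecast. Section 1.2 cites 87.2% local-regional control at 3 years in an inoperable series. That is 38 × 0.128 = 4.9 failures, against 38 × 0.10 = 3.8 assumed for RODS by 2 years.
- Chemotherapy timing is left to the oncologist (Section 9.1.1), so overlap with the 1-month comparison cannot be assumed.
- Stopping at salvage shortens observation more in the arm with more failures and could hide its late events.

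**Conclusion.** The point holds for CTCAE-graded symptoms: no pre-treatment assessment is scheduled and no baseline rule is stated. The consequence is dilution of the objective 2.2.4 comparison in both arms, with no systematic advantage to either. The direction follows from the design. The size rests on assumed rates, an assumed test level and the assumption that every prior symptom is counted: power of 50% drops to 40%, 34% or 23% at 5%, 10% or 20% prevalence. Power is modest even with clean data, and the loss is small for grade 3 or higher events. This is a worthwhile correction to a secondary comparison, with no bearing on the primary endpoint. The absence of a cut-off at adjuvant or salvage therapy is not an error.

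**What to change.** 1. In Appendix II, mark adverse-event assessment in the pre-registration column, at the history and physical already required there.
2. In Section 13.5.3, state that a CTCAE event counts only if its grade exceeds that patient's baseline grade, in line with the PFT rule in Section 6.7.3.
3. Keep the comparison by assigned arm, without a cut-off at later therapy, as the main analysis. A table of events before the first adjuvant or salvage therapy may be shown as supportive, with a note that observation time can then differ by arm.

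The cost of items 1 and 2 is one extra form entry per patient at an existing visit. Item 3 is optional and needs a therapy start date and one table. For patients already treated, a baseline grade depends on what their pre-registration history recorded, and the report should say for how many it was available.
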